7.3. Unscheduled Visits

If, during the investigation, a subject requires an unscheduled visit to the clinical site, the following information will be collected, as appropriate:

- Chief complaint prompting the visit. If the reason is an adverse event, the applicable eCRF for the adverse event must be completed and subject record completed as appropriate.
- Date and time of the visit and all procedures completed at the unscheduled visit.
- Review of adverse event and concomitant medications.
- Documentation of any test article dispensed or collected from the subject, if applicable.
- Slit lamp findings (using the Slit Lamp Classification Scale).

If the Investigator withdraws a subject from the study, the final study visit case report forms must be completed indicating the reason(s) why the subject was withdrawn. The subject record must be completed documenting the date and primary reason for withdrawal and the study CRA notified.

Any ocular and non-ocular Adverse Events that are ongoing at the time of the study visit will be followed by the Investigator, within licensure, until they have resolved, returned to pre-treatment status, stabilized, or been satisfactorily explained. If further treatment i.e., beyond licensure is required, the subject will be referred to the appropriate health care provider.

The following information will be collected during an unscheduled visit.

Clinical Study Protocol
Johnson & Johnson Vision Care, Inc.

Unscheduled Visit		
Step	Procedure	Details
U.1	Reason for unscheduled visit	Indicate if the only reason for the visit is that the subject requires additional test articles. If the reason is other than resupply of previously dispensed lenses, specify the reason for the visit.
U.2	Chief Complaints (if applicable)	Record the subject's chief complaints for reasons for the unscheduled visit.
U.3	Adverse Events and Concomitant Medications Review (if applicable)	Review any changes to the subject's medical history or concomitant medications from the previous study visit. Record any changes, and any adverse events.
U.4	Entrance VA (if applicable)	Record the entrance distance visual acuity (OD, OS) to the nearest letter.
U.5	Subjective Sphero-cylindrical Refraction (if applicable)	Perform bare-eye subjective sphero-cylindrical refraction with a phoropter (adopt the maximum plus to maximum visual acuity (MPMVA) approach and use the duo-chrome test for binocular balancing) and record the best corrected distance visual acuity to the nearest letter (OD, OS).
U.6	Slit Lamp Biomicroscopy (if applicable)	FDA Slit Lamp Classification Scale will be used to grade the findings. If the clearance of the fluorescein needs to be expedited, preservative-free rewetting drops may be instilled.
U.7	Dispensing (if applicable)	If the subject requires additional lenses to complete the wear period and is eligible to do so, provide additional lenses per the dispensing instructions given in the detailed study procedures.
U.8	Exit Visual Acuity (if applicable)	Record the subject's exit distance visual acuity (OD, OS) to the nearest letter.

NOTE: If the only reason for the unscheduled visit is that the subject requires additional test articles, only the dispensing information needs to be recorded.

7.4. Laboratory Procedures

Not applicable.

Clinical Study Protocol

Johnson & Johnson Vision Care, Inc.

8. SUBJECTS COMPLETION/WITHDRAWAL

8.1. Completion Criteria

Subjects are considered to have completed the study if they:

- provided informed consent.
- they are eligible.
- have not withdrawn/discontinued from the study for any reason described in section 8.2.
- completed all visits through the final visit (visit 5).
- If all visits were completed but an additional visit is considered necessary for subject care, follow the requirements for unscheduled visits in section 7.3.

8.2. Withdrawal/Discontinuation from the Study

A subject will be withdrawn from the study for any of the following reasons:

- Subject withdrawal of consent.
- Subject not compliant to protocol.
- Subject lost to follow-up.
- Subject no longer meets eligibility criteria (e.g. the subject becomes pregnant).
- Subject develops significant or serious adverse events necessitating discontinuation of study lens wear.
- Subjects who have experienced a Corneal Infiltrative Event (CIE).
- Investigator's clinical judgment regarding the subject safety reasons (that it is in the best interest of the subject to stop treatment).
- Subject misses any study visits.
- Subject not compliant with study lens wear schedule.
- Subject not successfully dispensed due to lack of efficacy and safety including poor vision, poor comfort or unacceptable fit.

For discontinued subjects, the Investigator will:

- Complete the current visit (scheduled or unscheduled).
- Complete the Final Evaluation, indicating the reason that the subject was discontinued from the study.
- Record the spherocylindrical refraction with best corrected distance visual acuity.
- Collect used test article(s) (worn or brought to the visit) from the subject and discard them, unless otherwise stated in section 7.2.
- Collect all unused test article(s) from the subject.
- Make arrangements for subject care, if needed, due to their study participation

Additional subjects may be enrolled if a subject discontinues from the study prematurely.

In cases where a subject is lost to follow-up, every possible effort must be made to contact the subject and determine the reason for discontinuation/withdrawal. The measures taken to follow up must be documented including two written attempts and a certified letter (or equivalent) as the final attempt.

Clinical Study Protocol

Johnson & Johnson Vision Care, Inc.

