		
returned to the clinical site (in solution, if possible) for shipping to the Sponsor. If lens damage is present, complete the Product Quality Complaint Form, store the lens in a labeled vial with saline and return it to the Sponsor.
 
 • Ensure the subject is aware of the correct lens power for each eye (label the lenses with R and L as appropriate). • Instruct the subject to bring their habitual spectacles to the next visit to wear following removal of the study lenses.
2.19	Schedule next visit	
Schedule the follow-up visit to occur in 7 ± 2 days (counting the day of this visit as day 0, the subject may return on day 5 through 9). Ensure the subject is instructed to wear the study lenses for at least 1 hour immediately prior to attending the follow-up visit.

VISIT 3

Visit 3 will occur 5 to 9 days following Visit 2. Subjects must present to this visit wearing the study lenses in both eyes, and lenses must have been worn for at least 1 hour prior to the visit.

Subjects must also bring their own habitual spectacles to this visit to wear following study lens removal.

Visit 3: Follow-up #1		
Step	Procedure	Details
3.1	Wear time and compliance	
Record the subjects wearing time and comfortable wearing time. Subjects must have worn lenses for at least 8 hours on at least 5 days during the dispensing period, and for at least 1 hour prior to attending this visit. Collect any unworn study lenses from the subject.

3.2	Review medical history and concomitant medications	
Record any changes to the subject's medical history (including adverse events) or concomitant medications.

Clinical Study Protocol
Johnson & Johnson Vision Care, Inc.

Visit 3: Follow-up #1																						
Step	Procedure	Details																				
3.3	Subject reported ocular symptoms	Record any subject reported ocular symptoms in response to a verbal open-ended symptoms questionnaire.																				
3.4	Follow-up PRO questionnaire	Subjects will complete CLUE and MRD questionnaires to assess their experience with the study lenses over the preceding wear period.																				
3.5	Follow-up NEI-RQL questionnaire	Ask subjects to complete the Follow-up NEI-RQL questionnaire regarding their experience with the study lenses over the preceding wear period.																				
3.6	Entrance visual acuity	Record the entrance Snellen VA for each eye while wearing the study lenses.																				

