3.11	Biomicroscopy	
The FDA Slit Lamp Classification Scale will be used to grade findings. If any slit lamp finding is graded as 3 or worse, the subject must be discontinued, an adverse event will be recorded, and the subject will be monitored as per the guidelines given in section 13.
 
Should the clearance of the fluorescein need to be expedited, preservative free rewetting drops or artificial tears may be instilled.
 
Study lenses may be discarded if there is no reason to store them following biomicroscopy.

3.12	Exit visual acuity	Record the exit monocular distance Snellen visual acuity for each eye with the subject wearing their habitual spectacle correction.
3.13	Washout period instructions	
Instruct the subject to wear only their habitual spectacle correction between this visit and the start of Visit 4. Subjects must not wear any contact lenses at any time during the washout period.

Clinical Study Protocol
Johnson & Johnson Vision Care, Inc.

Visit 3: Follow-up #1			
Step	Procedure	Details	
3.14	Schedule next visit	Schedule the next visit (Visit 3) to occur following a washout period of 7 ± 2 days (counting the day of this visit as day 0, the subject may return on day 5 through 9).	

VISIT 4

Visit 4 will occur 5 to 9 days following Visit 3. Subjects must present to this visit wearing their own spectacles, having not worn any contact lenses since Visit 3.

Visit 4: Spectacle Evaluation and Continuance			
Step	Procedure	Details	
4.1	Review medical history and concomitant medications	Record any changes to the subject's medical history (including adverse events) or concomitant medications.	
4.2	Subject reported ocular symptoms	Record any subject reported ocular symptoms in response to a verbal open-ended symptoms questionnaire.	
4.3	Spectacle PRO questionnaire	Subjects will complete CLUE vision and MRD questionnaires to assess their vision experience with their habitual spectacles over the preceding wear period.	
4.4	Spectacle NEI-RQL questionnaire	Ask subjects to complete the NEI-RQL questionnaire regarding their experience with their habitual spectacles over the preceding wear period.	
4.5	Entrance visual acuity	Record the entrance Snellen VA for each eye while wearing their spectacles.	

Clinical Study Protocol
Johnson & Johnson Vision Care, Inc.

Visit 4: Spectacle Evaluation and Continuance																							
Step	Procedure	Details																					

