5.1	Wear time and compliance	Record the subjects wearing time and comfortable wearing time. Subjects must have worn lenses for at least 8 hours on at least 5 days during the dispensing period, and for at least 1 hour prior to attending this visit. Collect any unworn study lenses from the subject.
5.2	Review medical history and concomitant medications	Record any changes to the subject's medical history (including adverse events) or concomitant medications.
5.3	Subject reported ocular symptoms	Record any subject reported ocular symptoms in response to a verbal open-ended symptoms questionnaire.
5.4	Contact lens preference and correction ranking questionnaire	Subjects will complete a questionnaire regarding their preference between the two contact lenses worn in this study (first contact lenses worn vs second contact lenses worn, or no preference). Subjects will also be asked to rank all three corrections worn in this study (first contact lenses worn, second contact lenses worn, and own spectacle correction) in order of preference.
5.5	Follow-up PRO questionnaire	Subjects will complete CLUE and MRD questionnaires to assess their experience with the study lenses over the preceding wear period.
5.6	Follow-up NEI-RQL questionnaire	Ask subjects to complete the Follow-up NEI-RQL questionnaire regarding their experience with the study lenses over the preceding wear period.
5.7	Entrance visual acuity	Record the entrance Snellen VA for each eye while wearing the study lenses.

Clinical Study Protocol
Johnson & Johnson Vision Care, Inc.

Visit 5: Follow-up #2																							
Step	Procedure	Details																					

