5.12	Biomicroscopy	
The FDA Slit Lamp Classification Scale will be used to grade findings. If any slit lamp finding is graded as 3 or worse, an adverse event will be recorded and the subject will be monitored as per the guidelines given in section 13.
 
Should the clearance of the fluorescein need to be expedited, preservative free rewetting drops or artificial tears may be instilled.
 
Study lenses may be discarded if there is no reason to store them following biomicroscopy.

FINAL EVALUATION

The final evaluation will ordinarily take place immediately following the last scheduled follow-up visit per the study protocol. It may also take place at any point the subject discontinues the study or is terminated from the study.

Final Evaluation		
Step	Procedure	Details
F.1	Final Exam Form	Indicate if the subject completed the study successfully. If subject discontinued from the study, indicate the reason.
F.2	Exit Refraction	
Perform bare-eye subjective spherocylindrical refraction with a phoropter and record the best-corrected distance visual acuity (OD and OS) to the nearest letter.
 
Note: This step is not necessary if the subject was exited due to screen failure.

Clinical Study Protocol
Johnson & Johnson Vision Care, Inc.

Final Evaluation		
Step	Procedure	Details
F.3	Exit Slit Lamp Biomicroscopy (for subjects that are discontinued early)	
FDA Slit Lamp Classification Scale will be used to grade the findings.
 
If the clearance of the fluorescein needs to be expedited, preservative-free rewetting drops or saline may be instilled. This step is not necessary if the subject was exited due to screen failure.
 
Note: This step is not necessary if the subject was exited due to screen failure, or if biomicroscopy was performed as part of the final follow-up visit procedures (i.e., immediately prior to the final evaluation).

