10. DEVIATIONS FROM THE PROTOCOL

Investigator will notify study sponsor upon identification of a protocol deviation. Protocol deviations must be reported to the sponsor within 24 hours after discovery of the protocol deviation. The Investigator will report deviations per IRB/IEC requirements. All deviations will be tracked, and corrective actions implemented as appropriate.

If it becomes necessary for the Investigator to implement a deviation in order to eliminate an immediate hazard to the trial subject, the Investigator may implement the deviation immediately without notification to the sponsor. Within 24 hours after the implemented deviation, the Investigator must notify and provide the rationale to the Sponsor and, as required, the IEC/IRB.

If the deviation potentially impacts the safety of patient or changes the technical integrity of the study, then it must be reported to IEC/IRB. This is a "Major Deviation". Deviations that contradict the information contained in the Informed Consent/Accent forms will be considered Major Deviations.

Minor deviations have no substantive effect on patient safety or technical integrity of the study. They are often logistical in nature.

Protocol waivers are prohibited.

Clinical Study Protocol
Johnson & Johnson Vision Care, Inc.

Table 6 lists examples of deviations that will constitute major and minor protocol deviations for this study.

Table 6: Examples of major and minor protocol deviations

Deviation category	Major deviation	Minor deviation
Out-of-window visit	Visit attended > 3 days out of visit window defined in study procedures	Visit attended \leq 3 days out of visit window defined in study procedures
Unanswered PRO questions	For questionnaires where data is related to a primary or secondary endpoint, > 2 PRO questions are unanswered (i.e., left blank).	For questionnaires where data is related to a primary or secondary endpoint, \leq 2 PRO questions are unanswered (i.e., left blank). For questionnaires where data where data is not related to a primary or secondary endpoint, any PRO questions are unanswered (i.e., left blank).
Non-compliance with wear schedule	Subject does not wear study lenses for at least 8 hours on at least 5 days of a study lens wear period. Subject wears their habitual contact lenses during any of the study lens wear periods. Subject wears contact lenses during the wash-in or washout periods.	Subject does not wear study lenses for at least 1 hour prior to attending a follow-up visit.

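### Section 8.2, read literally, withdraws a subject for a period-1 wear lapse that Section 10 sends to cohort review; where it is followed, the ITT tests lose period-2 and preference data (minor, cheap to fix)

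*Combined protocol and SAP*

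**What the plan says.** **Withdrawal.** Section 8.2 is worded as mandatory. Its reasons include "Subject not compliant with study lens wear schedule" and, as a separate bullet, non-compliance with the protocol in general. A discontinued subject finishes the visit in progress and goes to the Final Evaluation. That consists of a completion form, a slit lamp examination if not already done, and an exit refraction: "Perform bare-eye subjective spherocylindrical refraction with a phoropter and record the best-corrected distance visual acuity (OD and OS) to the nearest letter". It has no ETDRS acuity through a study lens, no CLUE and no preference question.

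**Visit steps.** Step 3.1 says "Subjects must have worn lenses for at least 8 hours on at least 5 days during the dispensing period" and does not say what follows if this is not met. Step 3.11, on the slit lamp, does: "If any slit lamp finding is graded as 3 or worse, the subject must be discontinued". For the washout, the Visit 4 preamble says "Subjects must present to this visit wearing their own spectacles, having not worn any contact lenses since Visit 3", and step 4.8 asks the site to confirm eligibility to continue. At step 5.4, "Subjects will complete a questionnaire regarding their preference between the two contact lenses worn in this study"; Table 3 schedules this at no earlier visit.

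**Deviations.** Table 6 in Section 10 gives as a major deviation "Subject does not wear study lenses for at least 8 hours on at least 5 days of a study lens wear period". The text below the table leaves Per-Protocol exclusion to cohort review.

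**Analysis.** Section 14.3 defines ITT as all randomised subjects whatever their later withdrawal or deviation. Per-Protocol requires both completing all visits and having no substantial deviation. The primary hypothesis, S1 (CLUE vision) and S3 (preference) are tested on ITT, and S2 (toric against spectacles) on Per-Protocol. Section 14.9 rules out imputation.

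**The concern.** An ITT set that disregards deviations is useful only if deviating subjects are still measured. A subject withdrawn at Visit 3 for too little wear gives one period of data in a two-period crossover and no preference answer. The trigger arises after randomisation and may be related to the lens: a subject may wear the first lens too little because vision or comfort was poor.

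The mixed models for acuity and CLUE can use a subject with period 1 only. They are valid if missingness depends only on data in the model, and wear compliance is not in the model. S3 has one response per subject, so the withdrawn subject is simply absent.

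Withdrawal also settles Per-Protocol status automatically, because that set requires all visits. The decision Section 10 gives to cohort review is then made at the site. At stake are a small selective loss of data in three tests and different handling of the same event between sites.

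**Working it through.** **1. The texts side by side.** Table 6, the cohort-review sentence and the two-part Per-Protocol definition make most sense if some subjects with a wear lapse finish the study. Section 8.2 taken literally means that a lapse found at Visit 3 ends participation. Step 3.1 does not settle it. A lapse found at Visit 5 costs no endpoint data, because that visit is completed.

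| Item | Lapse found at Visit 3, Section 8.2 followed |
|---|---|
| Period-1 HLHC VA and CLUE | kept (steps 3.4 and 3.7) |
| Visit 4 spectacle VA | lost; S2 is Per-Protocol, so this is not an ITT loss |
| Period-2 HLHC VA and CLUE | lost |
| Preference (S3) | lost; subject absent from the test |

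**2. The plan's own figures.** Inputs from Section 14.2: n = 153, two-sided alpha 0.05, SD of the difference = SD × √(2(1−ICC)). A noncentral-t paired test gives 0.823 / 0.876 / 0.927 for a difference of −0.025, SD 0.09 and ICC 0.3 / 0.4 / 0.5, as in Table 8. For CLUE (difference 5, SD 20, ICC 0.4 / 0.5 / 0.6) it gives 0.801 / 0.867 / 0.930, as in Table 9. Enrolment is 153 / 0.9 = 170.

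**3. Assumed loss.** The documents give no lapse rate. Let f be the fraction with period 1 only, equal in both sequences: 5% (half the 10% all-cause dropout allowance) or, as a ceiling, 10% (all of it).

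**4. Bias in the lens contrast.** Completers have effect dc and withdrawn subjects dw. The effect with full follow-up is dc + f(dw−dc). Under compound symmetry with four sequence-by-period means, the period-1 contrast equals that value. The period-2 contrast comes from completers, adjusted through the correlation with period 1, and equals dc − ICC × f(dw−dc). The average of the two differs from the full-follow-up effect by f(dw−dc)(1+ICC)/2 in size. It is zero if dw = dc and conservative if the withdrawn benefit more.

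The 95% half-width for the primary is t(0.975, 152) × 0.09 × √(2(1−ICC)) / √153 = 0.0170 / 0.0157 / 0.0144 at ICC 0.3 / 0.4 / 0.5. For CLUE it runs from 2.57 (SD 18, ICC 0.6) to 3.85 (SD 22, ICC 0.4).

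| Overstatement of toric benefit | f = 5% | f = 10% |
|---|---|---|
| VA (dc = −0.025), no effect in withdrawn | 0.0008–0.0009 | 0.0016–0.0019 |
| VA, effect reversed | 0.0016–0.0019 | 0.0033–0.0038 |
| VA, share of half-width | 5–13% | 10–26% |
| CLUE (dc = 5, ICC 0.4–0.6), no effect | 0.175–0.20 | 0.35–0.40 |
| CLUE, effect reversed | 0.35–0.40 | 0.70–0.80 |

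Example: f = 0.10, reversed, ICC 0.5 gives 0.10 × 0.050 × 1.5 / 2 = 0.00375 logMAR.

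**5. Precision.** Against full follow-up of the same subjects, the interval widens by √{[(1−ICC) + (1+ICC)/(1−f)]/2}. At f = 5% this is 1.017 (ICC 0.3) to 1.021 (ICC 0.6); at f = 10%, 1.035 to 1.043.

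**6. Preference.** Table 7 gives 49 against 17, odds 2.88, a share of 49/66 = 0.742 among those with a preference. If 5% are unobserved and split evenly, the full-group share is 0.95 × 0.742 + 0.05 × 0.5 = 0.730, odds 2.71; if their preference is reversed, 2.55. At 10% the odds are 2.55 and 2.27.

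**7. Carryover if washout violators were kept.** If a fraction g carries over with a differential effect λ, the period-2 contrast shifts by gλ and the lens contrast by gλ/2. With g = 5–10% and λ equal to the whole planned effect, the shift is 0.0006–0.0013 logMAR or 0.13–0.25 CLUE points.

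**The case against.** The strongest reply is that the protocol does not mean Section 8.2 literally. Its general non-compliance bullet would otherwise withdraw a subject for a visit one day out of window, which Table 6 calls minor. Where the protocol wants discontinuation at a visit, the step usually says so, and step 3.1 does not. This stands. A reader might infer that period-2 and preference data are certain never to be collected, but the documents do not support that. They support a conflict, with the loss occurring where a site follows Section 8.2.

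Second, period-1 acuity and CLUE are recorded at Visit 3 before any exit. If poor vision with the first lens caused the low wear, that outcome is already in the same endpoint's model. This also stands in large part: the absence of wear compliance from the model does not by itself break the missing-data assumption. The assumption is untested, and the argument does not help S3.

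Third, a reader might infer that washout violators should be kept on the same grounds. The case there is weaker. Their withdrawal rests on the general non-compliance bullet, since no study lens is worn in the washout. Section 4.2 also gives reduction of carryover as a purpose of the washout. For S2 the plan expects no carryover in objective acuity, but it says nothing of the kind for CLUE or preference, and the carryover figures above do not cover S3.

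Finally, the 10% dropout allowance and the option to replace subjects protect planned power if lapses fall within that allowance. That is correct, although replacement does not undo selective loss.

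**Conclusion.** The point holds as a conflict between Section 8.2 and the Section 10 route for wear-schedule lapses found at Visit 3, with a small selective loss of ITT data where Section 8.2 is applied. S3 is the only one of the three ITT tests that loses the subject completely.

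The size is minor. This point makes no stated power or sample size wrong. The largest primary bias, 0.0038 logMAR, requires the whole dropout allowance to be such lapses and the lens effect in those subjects to be fully reversed. Even then it is about a quarter of the confidence-interval half-width, and the preference odds stay well above 1. A reader might infer that the ITT results would be unreliable or could flip; no scenario computed here shows that.

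The figures rest on assumed rates of 5–10%, compound symmetry, equal loss in the two sequences and the plan's own effect sizes.

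**What to change.** Amend Section 8.2 so that non-safety non-compliance with the study lens wear schedule does not by itself end participation, and refer to this in step 3.1. These subjects go on to Visits 4 and 5, their acuity, CLUE and preference data enter ITT, and the deviation is dealt with by Per-Protocol exclusion at cohort review. Exits for safety, eligibility, consent, missed visits, loss to follow-up and failed dispensing stay as they are.

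The cost is a few lines of text and no visits beyond the five in Table 3. The downside is a slight dilution of the lens contrast from subjects who wore a lens too little. The documents give no basis for putting a figure on it.

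Keeping washout violators is optional, because it may bring carryover into CLUE and preference. If they are kept, repeat the primary, S1 and S3 analyses on the Per-Protocol set as a check.
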